#### **4.5.2.2. Impact of COVID-19 Pandemic on Adverse Event Reporting**

The number of participants with suspected, probable or confirmed for COVID-19 infection will be reported. This display will also summarise the number of participants with a COVID-19 diagnosis test performed and the number of participants with positive, negative, or indeterminate results.

Additionally, a listing of COVID-19 assessments and symptoms for participants with COVID-19 AEs will be generated.

#### **4.5.2.3. Cardiovascular Events and Deaths (All Causes)**

Cardiovascular events and deaths (all causes) will be captured on targeted CV event eCRF pages for the following AEs and SAEs:

- Arrhythmias
- Congestive heart failure
- Cerebrovascular events/stroke and transient ischemic attack
- Deep venous thrombosis/pulmonary embolism
- Myocardial infarction/unstable angina
- Peripheral arterial thromboembolism
- Pulmonary hypertension
- Revascularization
- Valvulopathy
- Death (all causes)

A summary table will be generated of all reported cardiovascular events and deaths (all causes). Separate patient profiles will also be provided of participants with each of the above listed events.

#### **4.5.3. Additional Safety Assessments**

##### **4.5.3.1. Laboratory Data**

Summaries of laboratory data including chemistry and haematology parameters, and liver function test data will be based on GSK Core Data Standards and unless otherwise specified will include on-treatment and post-treatment data. Change from baseline values for clinical chemistry and haematology will be summarised in separate tables using descriptive statistics.

Summaries of the number and percentage of participants with worst-case changes from baseline with respect to both the Normal Range (NR) and Potential Clinical Importance (PCI) criteria (for all lab tests where a PCI ranges are defined in the OPS) will be generated separately. Decreases to low, changes to normal or no changes from baseline,

and increases to high will be summarized for the worst-case post-baseline. If a participant has a decrease to low and an increase to high during the same time interval, then the participant is counted in both the “Decrease to Low” categories and the “Increase to High” categories. Participants with a missing baseline value are assumed to have been normal at baseline and participants with no data for a given lab test post-baseline (following first dose of study treatment) will be excluded from this summary.

Separate summary tables for haematology, and chemistry laboratory tests will be produced. These summaries will also be presented by Background INCS use subgroup (defined within Section 4.11.1).

Liver function laboratory tests will be included with chemistry lab tests.

Any liver stopping or liver monitoring events which occur during the study will be summarised. Summaries of hepatobiliary laboratory events including possible Hy’s law cases will also be provided in addition to what has been described above. Possible Hy’s law cases are defined as any elevated alanine aminotransferase (ALT)  $\geq 3 \times$  upper limit of normal (ULN), total bilirubin  $\geq 2 \times$  ULN and alkaline phosphatase (ALP)  $< 2 \times$  ULN/missing. Total bilirubin  $\geq 2 \times$  ULN can be within 28 days following the ALT elevation and if direct bilirubin is available on the same day, it must be  $\geq 35\%$  of total bilirubin.

ALP  $< 2 \times$  ULN/missing means it is satisfied unless the ALP is  $\geq 2 \times$  ULN at the time of bilirubin elevation (within 28 days following the ALT elevation). The summary will be produced for worst-case post-baseline only. A listing will be generated of all chemistry and liver function tests in participants who met the protocol defined liver stopping or liver monitoring criteria.

An e-DISH plot of maximum post-baseline total bilirubin versus maximum post-baseline ALT will be created.

Additionally, the worst-case urinalysis results post-baseline (including both on-treatment and post-treatment data) relative to baseline will be reported. The percentages are based on the number of participants in each treatment group with data for a given test post-baseline. Participants with a missing baseline value are to be assumed to have a negative baseline value.

#### 4.5.3.2. ECG

Summaries of ECG data will be based on GSK Core Data Standards. The number of abnormal and clinically significant 12-lead ECG results post-baseline will be produced by visit, also showing the worst recorded value post-baseline (including on-treatment and post-treatment data). Change from baseline values for each ECG parameter will be summarised using descriptive statistics.

The QTc data analysis will use the collected QTc values based on the Fridericia formula (QTcF). QTcF values will be rounded to the nearest integer and values will be categorized into the following CTCAE grade and ranges: Grade 0 [REDACTED] Grade 1 [REDACTED], Grade 2 [REDACTED] and Grade 3 [REDACTED] Summaries of grade increase will be provided. These summaries will display the number and percentage of participants with any grade increase, increase to grade 2 and increase to

grade 3 for the worst-case post-baseline only. Missing baseline grade will be assumed as grade 0. Participants with QTc data post-baseline (following first dose of study treatment) will be excluded from this summary.

The changes in QTc values will be categorized into the clinical concern ranges which are specific to changes in QTc: >30-≤60 and >60 msec. A summary of change in QTc value will display the number and percentage of participants with a change within each range for the worst-case post-baseline only. Participants with missing baseline values or with no QTc data post-baseline (following first dose of study treatment) will be excluded from this summary.

A listing will be generated of all ECG results in participants who met the protocol defined QTc stopping criteria.

#### **4.5.3.3. Vital Signs**

Summaries of vital signs data [systolic blood pressure (SBP), diastolic blood pressure (DBP) and heart rate] will be based on GSK Core Data Standards. Change from baseline values for SBP, DBP and heart rate will be summarised using descriptive statistics.

Summaries of grade increase from baseline in SBP and DBP will be provided separately. These summaries will display the number and percentage of participants with any grade increase, increase to Grade 2 and increase to Grade 3 for worst-case post-baseline only.

The grade definition for SBP is: Grade 0 cci [redacted] Grade 1 cci [redacted], Grade 2 cci [redacted] [redacted], Grade 3 cci [redacted]. The grade definition for DBP is: Grade 0 cci [redacted], Grade 1 cci [redacted] [redacted] Grade 2 cci [redacted], Grade 3 cci [redacted]. The summaries will be produced for worst-case post-baseline only (including both on-treatment and post-treatment data). A missing baseline grade will be assumed as grade 0. Participants with no SBP or DBP data post-baseline (following first dose of study treatment) will be excluded from this summary.

## **4.6. Immunogenicity**

An immune response to a therapeutic drug can lead to generation of anti-drug antibodies within the blood. For the immunogenicity assessment, two types of antibody assays will be performed, a binding anti-drug antibody (ADA) assay and a neutralizing antibody (NAb) assay.

For the binding ADA assay, there will be three testing steps: screening, confirmation and titration. The screening assay produces a result of positive or negative relative to a screening assay cut point. Positive samples continue with the confirmation assay, which also produces a result of positive or negative relative to a confirmation cut point. For positive confirmation samples, a titre value will also be obtained to quantify the degree of binding in a titration assay. Participants with a positive confirmation result will be positive for the binding ADA assay. Participants who test positive for the binding ADA assay, will be tested for the NAb assay, which also reports results as positive or negative.

Immunogenicity data will be summarised for all participants in the Safety analysis set. For the binding ADA assay, confirmation results at each visit will be categorised as negative or positive and summarised. NAb assay results will also be summarised.

The highest binding ADA assay confirmatory result obtained post-baseline for a participant (including both on-treatment and post-treatment data), will be summarised with a positive result being considered higher than a negative one, participants with both positive and negative results will be identified in the positive category. Descriptive statistics for titre results will also be presented. In addition, the highest NAb assay result during the same period will be summarised (again with a positive result being considered higher than a negative one and participants with both positive and negative results will be identified in the positive category).

A summary of treatment emergent positive confirmatory binding ADA assay results in the subset of participants who did not have a positive confirmatory binding ADA assay result prior to the first dose of study treatment will also be presented.

All immunogenicity results (i.e. binding ADA screening and confirmatory assay results, titre values and NAb results) will be listed.

## 4.7. Pharmacodynamic Analyses

The pharmacodynamic endpoints for analysis are:

- Absolute and ratio to baseline in blood eosinophil count at Weeks 4, 8, 24 and 52

### 4.7.1. Definition of Endpoint(s)

Blood eosinophil counts will be measured during the course of the study over the 52 weeks treatment period. Blood eosinophil counts will be log-transformed before analysis. Zero values for the baseline blood eosinophil count as well as for blood eosinophil count during the study will be replaced by 0.005 GI/L prior to log transformation.

### 4.7.2. Main Analytical Approach

The treatment effect to be estimated will be the comparison of mepolizumab 100 mg SC + SoC to placebo + SoC. The population of interest will be the entire trial population (patients meeting the study inclusion/exclusion criteria with a diagnosis of CRSwNP / ECRS) who are randomised and receiving study treatment (ITT analysis set).

The summary measure of treatment effect will be the difference in mean scores (ratio of the effect) between mepolizumab and placebo at Weeks 4, 8, 24 and 52.

Only data collected while the participant was on-treatment will be used in the analysis (applying a ‘while on-treatment strategy’). Blood eosinophil counts taken more than 28 days following the last dose of study treatment will not be included in the analysis. Missing data will be assumed to be missing at random (MAR).

The ratio to baseline in blood eosinophil count will be analysed using mixed models repeated measures adjusting for covariates of treatment group, log of baseline blood eosinophil count, background INCS use, country and time point, plus interaction terms for time point by baseline and time point by treatment group.

An unstructured covariance structure for the R matrix will be used by specifying ‘type=UN’ on the REPEATED line. The Kenward and Roger method for approximating the denominator degrees of freedom and correcting for bias in the estimated variance-covariance of the fixed effects will be used. The estimated mean for each treatment group will be calculated from the model using the observed marginal distributions of the sample covariates (OM option in LSMEANS statement).

Model-estimates of the absolute mean and mean ratio to baseline will be back-transformed and presented with corresponding standard errors on the log scale for each treatment group by visit. Estimated treatment differences (Mepolizumab/Placebo) with corresponding 95% CIs and p-values will also be presented.

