1.2. Schema

1.3. Schedule of Activities (SoA)

	Procedure	Pre-screening ¹	Screening ¹	Treatment															
				0	1	2	3	4	5	6	7	8	9	9a	10	11	12	13	14
Visit		0	up to 28 ±7 days prior to Day 1	1	29	57	85	113	141	169	197	204 (±1day)	225	253	281	309	337	365	28 ±7 days post last dose
Study Day (visit window ±7 days)				0	4	8	12	16	20	24	28	29	32	36	40	44	48	52	
Week																			
Screening/baseline	Informed consent	X																	
	Blood collection for eosinophils eligibility confirmation (if required) ²	X																	
	Inclusion and exclusion criteria		X																
	Demography		X																
	Full physical exam including height and weight		X																
	Medical history (includes substance usage and family history of premature CV disease CRSwNP/ECRS and asthma therapy, asthma and exacerbation history and concomitant medications)			X															
	SAE Review			X															
	History of HIV and Hep B, Hep C screen				X														
	Past and current medical conditions including cardiovascular medical history					X													
	History of systemic CS use for NP					X													
	History of NP surgery						X												

	Procedure	Pre-screening ¹	Screening ¹	Treatment																	
				0	1	2	3	4	5	6	7	8	9	9a	10	11	12	13	14	15	
Visit	Study Day (visit window ± 7 days)		up to 28 ± 7 days prior to Day 1	0	1	2	3	4	5	6	7	8	9	9a	10	11	12	13	14	15	IP DISC / EW Visit
Study Day (visit window ± 7 days)						1	29	57	85	113	141	169	197	204 (± 1 day)	225	253	281	309	337	365	28 ± 7 days post last dose
Week						0	4	8	12	16	20	24	28	29	32	36	40	44	48	52	
	Parasitic screening ³					X															
	Screening 12-lead ECG					X															
	Screening Vital signs					X															
	Assessment of endoscopic NP score ¹¹					X															
	Assessment of VAS for NP symptoms including Overall VAS ⁶					X															
	Assessment of Screening CT ⁴					X															
	Screening Laboratory assessments: Haematology (including blood eosinophils) and chemistry (including liver chemistries)					X															
	Screening Urinalysis					X															
	Urine pregnancy test (WOCBP only) ⁵					X															
	Dispense and Train in the use of eDiary ⁶					X															
	Register visit	X	X	X	X	X	X	X	X	X	X	X	X		X	X	X	X	X	X	
	Randomisation					X															
	Genetics sample ⁷														X						
Efficacy	Assessment of NP Surgery					X	X	X	X	X	X	X	X		X	X	X	X	X	X	

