13. Blood for PK will be collected at Visits 3 (pre-dose), 9 (pre-dose) and 15 (or IP discontinuation/early withdrawal). In addition, one post-dose PK collection will be at Week 29 (Visit 9a, one week after dose at Visit 9) with a collection visit allowance of ± 1 day. As for Week 29, blood sample will be collected from up to approximately first 30 Japanese and all Chinese participants randomised, no PK samples will be collected outside Japan and China
14. For participants who are willing to perform self-administration within the Japanese participants cohort: self-administer from Week 32 onwards (after receiving at least two trainings by investigator or delegate beforehand)
15. Laboratory assessments: Haematology (including blood eosinophils) will be taken at visits 1, 2, 3, 4, 7, 8, 10, 13, 14, 15 (or IP discontinuation/Early Withdrawal Visit)
16. Laboratory assessments: chemistry (including liver chemistries) will be taken at visits 1, 2, 3, 4, 7, 10, 13, 15 (or IP discontinuation/Early Withdrawal Visit)
17. ACQ-5 and SNOT-22 will be performed at baseline (visit 2), 3, 4, 5, 6, 7, 8, 11, 15, IP discontinuation/Early Withdrawal Visit

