4.4. End of Study Definition

A participant is considered to have completed study treatment if he/she receives study treatment at Visit 14 (Week 48). A participant is considered to have completed the study if he/she has completed all phases of the study including the last visit (Visit 15/Week 52) or the last scheduled procedure shown in the SoA, (Section [1.3](#)) whichever is earlier.

The end of the study is defined as the date of the last visit of the last participant in the study or last scheduled procedure shown in the SoA for the last participant in the trial globally, whichever is earlier.

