6.1. Study Intervention(s) Administered

Study intervention or treatment is defined as any investigational treatment(s), marketed product(s), placebo, or medical device(s) intended to be administered to a study participant according to the study protocol.

A liquid formulation of mepolizumab will be provided as pre-filled syringes in a safety syringe device (SSD) for this study. The liquid formulation has a distinct advantage over the lyophilised product as it does not require reconstitution, and the devices (upon commercial registration) will simplify and facilitate administration.

There will also be a matched safety syringe with placebo. Both active and placebo drug products are stored at 2-8°C condition, protected from light.

The study consists of up to 17 visits with a maximal total treatment duration of approximately 52 weeks and maximum study duration of approximately 56 weeks. Screened participants will enter a 4 weeks run-in period, followed by up to 52 weeks double-blind treatment period.

Participants who are successfully enrolled into the study will be randomised in a 1:1 ratio into one of two treatment groups, receiving a total of thirteen doses (one every four weeks):

- Group 1: 100 mg SC of mepolizumab on top of SoC
- Group 2: Placebo SC on top of SoC

The end of study assessments for each individual participant will be performed at Visit 15 (Week 52), 4 weeks following the last dose of IP.

Study Treatment	
Product name:	Mepolizumab Injection, 100 mg/mL
Device:	Safety syringe
Formulation description:	100 mg/mL mepolizumab with sodium phosphate, citric acid, sucrose, Disodium EDTA, Water for Injection and polysorbate 80
Dosage form:	Sterile, liquid formulation
Unit dose strength(s)/Dosage level(s):	100 mg/mL; 1.0 mL (deliverable)
Route of Administration	SC injection
Dosing instructions for HCP:	SC dose in thigh, abdomen or upper arm every 4 weeks
Dosing instruction for self-injection:	SC dose in thigh or abdomen every 4 weeks
Physical description: mepolizumab	Clear to opalescent, colourless to pale yellow to pale brown sterile solution for SC injection in a single-use, safety syringe
Physical description of injection device:	Single use, disposable safety syringe device assembled with a pre-filled syringe containing mepolizumab solution. A plastic needle cover shields the needle before and after injection to minimise the potential for needle stick injuries.

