### **4.5.1. Extent of Exposure**

Study treatment is administered (subcutaneously injected) approximately every 4 weeks and each dose viewed as providing therapeutic coverage for 4 weeks (28 days).

Duration of exposure is calculated based on the therapeutic coverage as follows:

- Duration (days) =  
(Last IP Administration Date – First IP Administration Date + 29)
- Duration (months) =  
(Last IP Administration Date – First IP Administration Date + 29)\*12/365.25
- Participant-years exposure =  
(Last IP Administration Date – First IP Administration Date + 29)/365.25

The extent of exposure to study treatment (mepolizumab/placebo) will be reported, including descriptive statistics of duration of exposure in addition to the number and percentage of participants exposed for  $\geq 1 < 3$ ,  $\geq 3 < 6$ ,  $\geq 6 < 9$ ,  $\geq 9 < 12$  and  $\geq 12$  months, based on each participant's duration of exposure rounded to the nearest whole month. The number of treatments administered and total participant-years exposure will also be summarised.

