#### **4.5.2. Adverse Events**

Adverse events analyses including the analysis of adverse events (AEs), Serious AEs (SAEs) and other significant AEs will be based on GSK Core Data Standards.

Adverse events will be coded using the standard Medical Dictionary for Regulatory Affairs (MedDRA dictionary), with the maximum severity of each AE determined by the investigator (as mild, moderate or severe).

An overview summary of AEs, including counts and percentages of participants with any AE, AEs related to study treatment, AEs leading to permanent discontinuation of study treatment, AEs leading to withdrawal from the study, AEs leading to dose delays, SAEs, SAEs related to study treatment, fatal SAEs, and fatal SAEs related to study treatment will be produced.

AEs will be considered on-treatment for at least 4 weeks (28 days) following the last dose of study treatment. AEs which occur more than 28 days following the last dose of study treatment will be considered as post-treatment. The number and percentage of participants experiencing at least one AE during the on-treatment and post-treatment periods will be summarised separately. Additionally, summaries of the number and percentage of participants with any on-treatment AEs by maximum severity will be produced. If an adverse event severity is missing, the severity is to be populated as 'UNKNOWN'.

The frequency and percentage of AEs will be summarized and displayed in two ways: 1) in descending order by SOC and PT and 2) in descending order by PT only.

Common AEs, defined as  $\geq 3\%$  (prior to rounding) in any treatment group, will be reported. The summary table will be displayed by PT only.

A separate summary will be provided for study treatment-related AEs. A study treatment-related AE is defined as an AE for which the investigator classifies the possible relationship to study treatment as "Yes". A worst-case scenario approach will be taken to handle missing relatedness data, i.e. the summary table will include events with the relationship to study treatment as 'Yes' or missing. The summary table will be displayed by SOC and PT.

All SAEs during the on-treatment and post-treatment periods will be tabulated based on the number and percentage of participants who experienced an event within each period. In addition, fatal and non-fatal SAEs will be reported separately.

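### The 28-day cut-off in the eosinophil analysis equals the scheduled gap from last dose to Week 52, so in-window Week 52 counts from treatment completers are dropped

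*SAP*

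**What the plan says.** SAP 4.7 names the pharmacodynamic endpoints as "Absolute and ratio to baseline in blood eosinophil count at Weeks 4, 8, 24 and 52". SAP 4.7.2 fits a repeated-measures model under a while-on-treatment strategy, treats missing counts as missing at random, and sets the boundary: "Blood eosinophil counts taken more than 28 days following the last dose of study treatment will not be included in the analysis".

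The boundary follows a convention used elsewhere in the SAP. Section 4.5.1 has "each dose viewed as providing therapeutic coverage for 4 weeks (28 days", and section 4.5.2 has "AEs which occur more than 28 days following the last dose of study treatment will be considered as post-treatment".

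The protocol fixes the timing:

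- The Schedule of Activities (section 1.3) puts Visit 14 (Week 48) at Day 337 and Visit 15 (Week 52) at Day 365, under the row label "Study Day (visit window ±7 days").
- Footnote 15 of the same section confirms that eosinophils are drawn at Visit 15: "Laboratory assessments: Haematology (including blood eosinophils) will be taken at visits 1, 2, 3, 4, 7, 8, 10, 13, 14, 15".
- Section 6.1 says that the end-of-study assessments "will be performed at Visit 15 (Week 52), 4 weeks following the last dose of IP".
- Section 4.4 says: "A participant is considered to have completed study treatment if he/she receives study treatment at Visit 14 (Week 48").

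**The concern.** The cut-off coincides with the nominal interval and leaves no tolerance, although the protocol allows each visit to move by a week either way. One day of in-window drift turns a treatment completer's Week 52 count from on-treatment to excluded. That does not fit the purpose of a while-on-treatment rule, which is to remove data collected after treatment has stopped. SAP 4.7.1 itself describes the counts as measured over a 52-week treatment period.

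The loss falls on the final timepoint only. At Weeks 4, 8 and 24 a completer still has later doses to come, so those counts cannot lie more than 28 days after the last one. What is at stake is mainly precision at Week 52. In addition, the retained samples are tilted towards shorter post-dose intervals.

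**Working it through.** **Inputs.** Visit 14 is Day 337 and Visit 15 is Day 365, each ±7 days (protocol 1.3). Counts are excluded when the gap exceeds 28 days (SAP 4.7.2). About 80 participants per arm are planned (SAP 1.2). Attendance patterns, 85% completion and the correlations below are assumptions, because the documents give none of them.

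**The plan's own figure.** 365 − 337 = 28 days, which reproduces the 4 weeks in protocol 6.1.

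**Permitted range.** With day deviations a at Visit 14 and b at Visit 15, each from −7 to +7, the gap is 28 + b − a. The minimum is 28 − 7 − 7 = 14 days and the maximum is 28 + 7 + 7 = 42 days. A count is lost whenever b > a. For a dose exactly on Day 337, that means in-window sampling on Days 366 to 372.

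**Share of completers losing the Week 52 count.**

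- Visit 15 booked from the actual dose date, symmetric deviations: (1 − share on the day)/2.
- Both visits scattering independently around their nominal days: (1 − P(a = b))/2. For uniform scatter P(a = b) = 1/15, giving (14/15)/2 = 46.7%.

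| Assumed attendance | Booked from dose date | Both visits scatter independently |
|---|---|---|
| 90% on the day | 5% | 9% |
| 80% on the day | 10% | 17–18% |
| 50% on the day | 25% | 31–37% |
| Normal, SD 1, 2, 3 days | – | 36.5%, 43.0%, 45.2% |
| Uniform over ±7 days | – | 46.7% |

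The ranges in the last column depend on whether off-day visits are all one day out or spread evenly over the window.

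**Counts lost.** With 0.85 × 80 = 68 completers per arm, 68 × 0.05 = 3.4 and 68 × 0.467 = 31.7, so about 3 to 32 per arm.

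**Precision at Week 52 among completers.** With fraction m lost and one earlier count correlating r with the Week 52 count, the ratio of standard errors is √[(1 − r²)/(1 − m) + r²].

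| | r = 0 | r = 0.5 | r = 0.7 |
|---|---|---|---|
| m = 0.05 | 1.026 | 1.020 | 1.013 |
| m = 0.467 | 1.369 | 1.287 | 1.203 |

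If only the four timepoints in SAP 4.7 enter the model, the nearest earlier count is Week 24. The later counts collected at Weeks 32, 44 and 48 would then contribute nothing.

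**Timing of retained samples.** The mean gap without the rule is 28.0 days. Booked from the dose date with 90% on the day and the rest one day out, the retained mean is 28 − 0.05/0.95 = 27.95 days. With both visits uniform, the retained deviations of −k days have weights (15 − k)/225 for k = 0 to 14. Their mean is 560/120 = 4.67 days, so the retained mean gap is 23.33 days.

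**The case against.** The strongest defence is that 28 days is a deliberate, coverage-based definition. SAP 4.5.1 and 4.5.2 use it, and SAP 4.2.3 uses the same threshold to call a visit off-treatment. On that view a count at 35 days is outside coverage whatever the reason. The convention is real, but in exposure and adverse-event reporting it assigns data to a period, whereas here it deletes a scheduled, in-window endpoint observation from someone the protocol counts as having completed treatment.

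A second point is that an exception for Visit 14 recipients is uneven. The IP discontinuation visit has the same ±7-day tolerance around 28 days after the last dose, so two participants sampled at the same interval could be classified differently. That stands as a cost of the fix. It does not justify losing the completers' data.

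Third, the magnitude rests on assumptions. This also stands. Protocol 6.1 describes Week 52 relative to the last dose, which fits booking from the dose date and the 5–25% column better than the uniform case. The no-borrowing figures are upper bounds, since the model uses the baseline count and earlier visits.

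Fourth, the stakes are low. The endpoint is outside H1–H8, no precision target is stated, the rule is the same in both arms, the counts remain in the haematology summaries (SAP 4.5.3.1), and no such cut is stated for the population PK/PD analysis (SAP 4.9.2). That limits the weight of the point and leaves the mismatch in place.

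Finally, the Output and Programming Specification, which holds further data-handling conventions (SAP 1), was not available and may contain a window rule. Such a rule would still have to be squared with the explicit SAP sentence.

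**Conclusion.** The concern holds. Followed as written, SAP 4.7.2 discards in-window Week 52 eosinophil counts from participants dosed at Visit 14 whenever the sample comes 29 or more days after that dose. Neither document states an exception.

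That such losses are possible follows from the calendar alone. Their size does not: 5% to 47% of completers spans the assumed attendance patterns, with 5% to 25% if Week 52 is booked from the dose date. The effect is mainly lost precision at one timepoint of a pharmacodynamic endpoint, plus some skew towards shorter post-dose intervals. No bias in the treatment ratio has been shown. The rule in SAP 4.7.2 does not affect the co-primary analyses or the study's power. The point is worth correcting because the remedy is small, but it does not threaten the trial's conclusions.

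**What to change.** Add one sentence to SAP 4.7.2, before unblinding: a Week 52 count taken within the Visit 15 window from a participant dosed at Visit 14 is on-treatment for this analysis, and the 28-day cut-off continues to apply to participants who discontinued IP early. If the Output and Programming Specification already has such a rule, state it in SAP 4.7.2.

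No new data are needed. The cost is that some counts taken up to 42 days after dosing are kept as on-treatment, that this analysis departs from the 28-day convention in SAP 4.5.1 and 4.5.2, and that early discontinuers sampled at the same interval are handled differently. The sponsor could check the same threshold in SAP 4.2.3 at the same time, although this change does not depend on it.
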